6.2.3 Post treatment

Participant's clinical status and outcome will be reviewed 30 days after study completion.

The following procedures will be collected:

- Interim medical history review /concomitant medications
- Physical Exam & Vital Signs
- Adverse Event/Unanticipated Problem assessment and recording

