3.1.3 Follow Up (Day 30)

Follow up data will be collected at 30 days following initiation of study treatment.

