3.2.2 Secondary Study Endpoints

1. Viral load measured in nasopharyngeal swab by Cycle Threshold at 0, 24, 48, and 72 hours after initiation of core warming
2. Duration of mechanical ventilation
3. Mortality

4 Study Population and Duration of Participation

All patients will have a diagnosis of COVID-19 requiring mechanical ventilation. Duration of intervention will be 72 hours. Follow-up will be to 30 days.

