4.4 Duration of Study Participation

Participants will be involved for approximately 30 days, including screening, treatment, and follow-up. After consent, patient participation in the intervention phase will last 72 hours for active treatment. The follow up for determination of outcome and duration of mechanical ventilation will occur at 1-month post-treatment. Additional data will be collected via chart review.

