5.1 Intervention Regimen

Patients who are randomized to core warming will have the esophageal heat transfer device placed in the ICU or other treatment area where patient is undergoing mechanical ventilation. The device will remain in place until the study is completed (72 hours). The device will be set to 42°C for the duration of the study period, with the exception of any elevations in patient temperature as described in section 3 above.

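### The follow-up point that sets the horizon for mortality and ventilation duration is Day 30 in some sections and about Day 33 in others, and the endpoint lists do not settle it

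*Combined protocol and SAP*

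**What the plan says.** Five places in the combined protocol and SAP bear on the date.

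- **Section 3.1.3**, whose heading already says Day 30: "Follow up data will be collected at 30 days following initiation of study treatment".
- **Section 6, schedule of procedures**: randomisation is on Day 0 and the follow-up column is Day 30, in one table for both arms.
- **Section 4.4**: "The follow up for determination of outcome and duration of mechanical ventilation will occur at 1-month post-treatment". The same section also says: "Participants will be involved for approximately 30 days, including screening, treatment, and follow-up".
- **Section 6.2.3**: "clinical status and outcome will be reviewed 30 days after study completion".
- **Section 5.1**, which shows what completion means: "The device will remain in place until the study is completed (72 hours".

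Section 6.4 runs adverse-event assessment at unscheduled visits to 30 days after the study, again without saying from which date. The opening text of section 4 is neutral: "Duration of intervention will be 72 hours. Follow-up will be to 30 days". It names no starting event.

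The endpoint lists in 3.2.2 and 7.1 give mortality and ventilation duration with no time point, and section 7.3 adds none.

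**The concern.** With no time point in the endpoint lists, the follow-up sentences are the only text that can fix the horizon for the two clinical secondary endpoints, and they disagree. The one sentence that names ventilation duration (section 4.4) uses the later date, against the schedule. Mortality is not named in any of these sentences; it is covered only by the general word outcome in 4.4 and 6.2.3.

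The anchors are also poor time zeros for a two-arm comparison. Controls do not have the device (section 3.1), so its start and end are not clearly dated for them. In the warming arm, randomisation comes before device placement (section 3.1.4), so treatment starts an unstated interval after randomisation. Treatment can also end early (sections 6.3 and 6.5), which moves any date counted from its end.

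At stake is whether both endpoints are read at one pre-stated date. The study team is not blinded (sections 5.2 and 8.6) and reviews data at 10 and 22 patients (section 8.7), so a horizon left open could be settled after outcomes are visible.

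**Working it through.** **Inputs from the documents.** Intervention 72 hours (sections 4 and 5.1); randomisation on Day 0 (schedule); 22 patients, 11 per arm (section 3.1). Treatment is taken to start on Day 0.

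**Dates under each rule**

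1. Schedule and section 3.1.3: 0 + 30 = Day 30. This reproduces the schedule's figure.
2. Section 4.4: treatment ends at 72/24 = Day 3. With a 30-day month, 3 + 30 = Day 33. With calendar months of 28 to 31 days, 3 + 28 = Day 31 to 3 + 31 = Day 34.
3. Section 6.2.3: completion at 72 hours is Day 3, and 3 + 30 = Day 33.
4. Early device removal under the section 4.4 rule, with a 30-day month: at 24 hours, 1 + 30 = Day 31; at 48 hours, 2 + 30 = Day 32.
5. Participation counted from screening on Day -1: 30 + 1 = 31 days under the first rule and 33 + 1 = 34 under the other two. The first fits the stated total of about 30 days better.

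A full course therefore gives two dates, 3 days apart: 3/30 = 10% of the window.

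**Effect on mortality.** The documents give no expected mortality, so I assume a 30-day mortality p of 20% to 60% and a constant hazard. Mortality at Day 33 is then q = 1 - (1 - p)^(33/30), and the extra deaths across both arms are 22(q - p).

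| p at Day 30 | q at Day 33 | Added points | Extra deaths of 22 |
|---|---|---|---|
| 20% | 21.8% | 1.8 | 0.39 |
| 30% | 32.5% | 2.5 | 0.54 |
| 40% | 43.0% | 3.0 | 0.66 |
| 50% | 53.4% | 3.3 | 0.74 |
| 60% | 63.5% | 3.5 | 0.77 |

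A second set of assumptions, 15 patients alive at Day 30 and a daily hazard of 0.5% to 2%, gives 15 × 3 × 0.005 = 0.2 to 15 × 3 × 0.02 = 0.9 deaths across both arms. Split equally, that is 0.11 to 0.45 per arm, and divided by 11 it is 1.0 to 4.1 percentage points.

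**Effect on the comparison.** Take assumed 30-day mortality of 30% in one arm and 40% in the other. The difference is 10.0 points at Day 30 and 42.99 - 32.45 = 10.5 points at Day 33, a change of about 0.5 points.

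**Effect on ventilation duration.** The cap moves from 30 to 33 days. This touches only patients still ventilated at Day 30.

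**The case against.** The best defence is that the intended date is clear enough. The schedule, the heading and text of 3.1.3, and the stated total participation all point to Day 30, while one month and approximately are loose words that tolerate a 3-day gap. A review date is also not a censoring rule: 4.4 and 6.2.3 say when status is looked up, not that later events count. Section 4.4 provides for chart review, so dated deaths and extubations could be cut at Day 30 whenever the chart is read. These are secondary endpoints in a 22-patient pilot without a power calculation.

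Much of this stands, and it lowers the severity. It does not remove the conflict, because no section states a Day 30 cut and the sentence that names ventilation duration gives the later date.

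A reader might also infer more than the documents support:

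- *Three separate horizons.* There are three wordings, but section 5.1 puts study completion at 72 hours. End of treatment and completion therefore coincide for a full course and part only if the device comes out early. The same sentence rules out reading completion as the end of follow-up, which would give about Day 60.
- *Different horizons by arm.* Section 3.1.2 applies a 72-hour study period to both arms, and study treatment in 3.1.3 could be read to include standard care. Nothing suggests that staff would date the arms differently. The time zero for controls is unclear, but a bias between arms is speculation.
- *A shift of 9.1 points.* One death in an arm of 11 is 1/11 = 9.1%. That is the step size of the estimate. The expected effect of 3 days is a fraction of one death spread over both arms.

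**Conclusion.** The concern holds as an inconsistency between written rules: wrong as written, minor severity. Section 3.1.3 and the schedule give Day 30. Sections 4.4 and 6.2.3 give about Day 33 (Day 31 to 34 for 4.4, depending on the length of the month), and 6.4 leaves the same doubt.

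The size is 3 days. The expected number of extra deaths is 0.4 to 0.8 of 22 with 30-day mortality of 20% to 60% and a constant hazard, or 0.2 to 0.9 under the second set of assumptions. All these rates are assumed; the documents supply none. If one horizon is used for everyone and the hazards are similar in the two arms, the between-arm difference hardly moves. The date conflict does not invalidate the design and does not touch the primary endpoint.

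**What to change.** Use one horizon, Day 30 after randomisation in both arms, in sections 3.1.3, 4.4, 6.2.3, 6.4 and 7.1, and carry the endpoint names into 3.2.2. This matches the schedule, gives both arms the same time zero, and cannot be moved by early device removal. Suggested endpoint names:

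- *30-day all-cause mortality*: death from any cause from randomisation to Day 30.
- *Ventilation duration from randomisation to Day 30*, with a stated rule for patients who die before Day 30. Without one, an early death scores as a short and apparently favourable duration, which could matter more than the 3 days. One option compatible with the Mann–Whitney test in section 7.3 is to rank deaths as worse than any duration in a survivor.

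Add one sentence saying that the chart may be reviewed after Day 30, provided that events are cut at Day 30 by their recorded dates. In 6.4 the change only fixes the date to which routine assessment runs; the separate provision in 8.2 for later, possibly related serious events is unaffected.

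The cost is wording. No visit or procedure is added, as long as the case report form holds the date of death and the date on which ventilation ended. The change should be made before the data review at 10 patients or, if that has passed, without reference to outcomes by arm.

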6.3 Rescue Therapy

The core warming device will be removed and replaced if at any time there is evidence of a potential device malfunction. The device can be easily removed and replaced during treatment if needed. Should evidence of continued malfunction occur after replacement of the study device, the device will be removed, allowing the patient to undergo the standard of care with respect to temperature monitoring and control.

6.4 Unscheduled Visits

The research team will assess for the occurrence of any adverse event(s)/unanticipated problem(s) should a patient present for any unscheduled visit after discharge, up through 30 days following the study.

6.5 Subject Withdrawal

Subjects may withdraw from the study at any time without impact to their care. They may also be discontinued from the study at the discretion of the Investigator for lack of adherence to study procedures or visit schedules, AEs, or should it become clinically necessary to deviate from the study protocol during the course of the study. The Investigator may also withdraw subjects who violate the study plan, or to protect the subject for reasons of safety or for administrative reasons. It will be documented whether or not each subject completes the clinical study. We will attempt to have one final visit or contact to follow up regarding adverse events for participants who withdraw prior to the 30 day follow up visit.

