6.5.1 Data Collection and Follow-up for Withdrawn Subjects

We will attempt to have one final visit or contact to follow up regarding adverse events for participants who withdraw prior to the 30 day follow up visit. During this contact they will be asked for permission to have the study team look into their survival status via their electronic medical records and publicly available means.

7 Statistical Plan

Primary Endpoint

The primary endpoint of this study will be the change in PaO₂/FiO₂ ratio at 0, 24, 48, and 72 hours after implementation of core warming of ventilated patients. This endpoint will be compared between patients receiving core warming and those randomized to undergo standard care (standard temperature management, with or without antipyretics as needed).

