7.4 Subject Population(s) for Analysis

All patients enrolled, randomized to a study arm, and completed in the study will be included for analysis.

8 Safety and Adverse Events

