8.5 Expedited Reporting of Events

Any study-related unanticipated problem posing risk to subjects or others, and any type of unanticipated serious adverse event or unanticipated adverse device effect, will be reported to the IRB in accordance with the institutional and FDA requirements. Investigators will use the appropriate SAE/UP CRF to record events and a line item will also be added to the AE log CRF.

The minimum necessary information to be provided at the time of the initial expedited event report includes:

• Study identifier• Study Center• Subject number• A description of the event• Date of onset	
• Current status• Whether study intervention was discontinued• The reason why the event is classified as serious• Investigator assessment of the association between the event and study intervention
---	--

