8.6 Unblinding Procedures

The study team will not be blinded to the randomization assignment. The study team will be instructed to maintain blinding for participants unless a participant has a clinical need to know their randomization assignment. The decision to unblind will be at the discretion of the study PIs and only if unblinding would change clinical care. Unblinding for safety reasons will be recorded in study records and it will be reported to the IRB and the funding sponsor at the time of continuing review.

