9.2 Data Collection and Management

Data will be collected by trained research staff using source documents and CRFs. Source and CRFs will be entered into a RedCap data management system. Participants will be assigned a Participant ID “PID” for use on CRF data collection for entry into the data management system to protect and ensure confidentiality.

Source data is all information, original records of clinical findings, observations, or other activities in a clinical trial necessary for the reconstruction and evaluation of the trial. Source data are contained in source documents. Examples of these original documents, and data records include: hospital records, clinical and office charts, laboratory notes, memoranda, subjects' diaries or evaluation checklists, pharmacy dispensing records, recorded data from automated instruments, copies or transcriptions certified after verification as being accurate and complete, microfiches, photographic negatives, microfilm or magnetic media, x-rays, subject files, and

records kept at the pharmacy, at the laboratories, and at medico-technical departments involved in the clinical trial.

The study case report form (CRF) is the primary data collection instrument for the study. All data requested on the CRF must be recorded. All missing data must be explained. If a space on the CRF is left blank because the procedure was not done or the question was not asked, write "N/D". If the item is not applicable to the individual case, write "N/A". All entries should be printed legibly in black ink. If any entry error has been made, to correct such an error, draw a single straight line through the incorrect entry and enter the correct data above it. All such changes must be initialed and dated. DO NOT ERASE OR WHITE OUT ERRORS. For clarification of illegible or uncertain entries, print the clarification above the item, then initial and date it. The study data will be stored indefinitely. A de-identified data set may be shared with the funding sponsor.

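### Section 6.5 allows study exit for an adverse event or clinical deviation, and nothing commits to collecting or analysing endpoint data after an investigator-initiated exit

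*Combined protocol and SAP*

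**What the plan says.** Section 6.5 (Subject Withdrawal) covers voluntary withdrawal and then investigator-initiated exit: "They may also be discontinued from the study at the discretion of the Investigator for lack of adherence to study procedures or visit schedules, AEs". The same sentence adds a clinically necessary deviation from the protocol as a ground. The next one says: "The Investigator may also withdraw subjects who violate the study plan, or to protect the subject for reasons of safety or for administrative reasons". Under 5.2 and 8.6 the people deciding know the arm: "The study team will not be blinded to the randomization assignment".

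Section 6.5.1, headed for withdrawn subjects, provides one attempted visit or contact about adverse events. It continues: "During this contact they will be asked for permission to have the study team look into their survival status via their electronic medical records", with publicly available sources as a further route. P/F, viral load and ventilation duration are not mentioned. They are the primary endpoint and two of the three secondary endpoints (Sections 7 and 7.1).

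Section 7.4 sets the analysis population: "All patients enrolled, randomized to a study arm, and completed in the study will be included for analysis".

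Two provisions deal with the device without mentioning exit. Section 6.3 removes it after continued malfunction and returns the patient to standard temperature care. Section 3.1.2 lowers the setting to 40°C if the patient reaches 39.8°C.

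**The concern.** Stopping a treatment and leaving a study are different events. A patient whose warming is stopped for falling blood pressure can still have blood gases recorded at 24, 48 and 72 hours. Section 6.5 offers study exit in that situation and does not mention the alternative.

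The situation is foreseeable. Section 11.1 lists vasodilation with higher vasopressor need, raised heart and metabolic rates, and esophageal injury among the risks. An adverse event or a necessary deviation can be related to how the patient is doing, and the decision is made with knowledge of the arm. If patients leave for such reasons and are then dropped from the analysis, the groups compared are no longer the groups randomized.

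The pilot is meant to inform larger studies (7.2), and what happens to patients after the device is stopped is part of what those studies would need to know.

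**Working it through.** The plan gives no exit rate, SD, effect size or power figure (7.2 says a power calculation could not be done accurately), so there is no figure to reproduce. The check is a reading of the rules, then the arithmetic that the group size alone allows.

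**1. What happens after each kind of event**

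| Event | Section | Device or procedure stopped without exit? | Later endpoint collection stated? |
|---|---|---|---|
| Repeated malfunction | 6.3 | Yes | No |
| Patient reaches 39.8°C | 3.1.2 | Setting lowered, no stop | No separate rule |
| Adverse event | 6.5 | Not stated; study exit offered | No |
| Clinically necessary deviation | 6.5 | Not stated; study exit offered | No |
| Withdrawn subject | 6.5.1 | Not applicable | Adverse events and, with permission, survival |
| Authorization revoked | 9.1 | Not applicable | Vital status, with permission |

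Section 8.2 continues adverse-event recording to Day 30, but that covers adverse events only. Sections 3.1.2, 4.4 and 6.2.2 describe routine and chart data in general terms and do not address patients who have exited.

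**2. From exit to analysis.** A patient discontinued from the study under 6.5 has, in ordinary language, not completed it. Section 7.4 then leaves that patient out, even if chart data could be retrieved.

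**3. Size of one exit.** Input: 11 patients per arm (3.1).

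- Share of an arm: 1/11 = 9.1%; two exits, 2/11 = 18.2%.
- Planned P/F times after baseline: 24, 48 and 72 hours. Exit before 24, 48 or 72 hours leaves 3, 2 or 1 of these unsecured.
- Recruitment ends at 22 randomized (4.5), and no replacement is stated. Section 7.2 asks for 10 per group: 11 − 1 = 10 meets that, 11 − 2 = 9 does not.

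**4. Precision.** With equal SDs, the standard error of a difference in means is proportional to √(1/a + 1/b), where a and b are the patients analysed per arm. Relative to 11 versus 11 the ratio is √[(1/a + 1/b)/(2/11)]:

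- 10 versus 11: √1.050 = 1.025, a rise of 2.5%
- 10 versus 10: √1.100 = 1.049, a rise of 4.9%
- 9 versus 11: √1.111 = 1.054, a rise of 5.4%
- 9 versus 9: √1.222 = 1.106, a rise of 10.6%

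**5. Price of keeping such patients.** If one warmed patient gets no benefit and the other ten get the full mean effect Δ, the arm shows (10/11)Δ = 0.909Δ, a dilution of 9.1%. A patient with partial benefit dilutes it less.

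**The case against.** The strongest reply is that the protocol already distinguishes stopping the device from leaving the study. Section 6.3 does so for malfunction, and the expedited report in 8.5 has its own item, "Whether study intervention was discontinued", separate from the completion record in 6.5. Section 6.5 is permissive, so no adverse event forces an exit. All of this stands. A reader might infer that the protocol never allows a device to be stopped without exit, or that adverse events lead automatically to exit; the text supports neither. What remains is that the distinction is not extended to adverse events or clinical deviations.

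A second reply is that 6.5.1 may cover only people who withdraw themselves, since asking permission suits a withdrawal of consent. The heading and "The Investigator may also withdraw subjects who violate the study plan, or to protect the subject for reasons of safety or for administrative reasons" point the other way, so the text is ambiguous. If the narrower reading is right, investigator-initiated exits have no specific endpoint follow-up rule at all.

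Third, a reader might infer that the endpoint data would be lost. That goes too far. Blood gases and ventilation times are largely routine care and would often be in the chart; 9.2 also requires that "All missing data must be explained"; and 6.2.2 mentions viral load at the end of treatment, which an early stop might prompt. The fair statement is that the data are not secured. A chart can be read later, but a 72-hour viral sample not taken cannot be recovered, and general chart-review wording does not override 7.4.

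Fourth, 5.1 says "The device will remain in place until the study is completed (72 hours", and a reader might combine this with 7.4 to conclude that stopping the device early makes a patient a non-completer. Section 5.1 describes how long the device stays in and does not define completion; 4.4 runs participation to about 30 days. The point here does not rely on that reading.

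Finally, it is tempting to say that sicker warmed patients would be removed and the result would favour warming. Section 6.5 applies to both arms, and nothing in the documents fixes a direction or a size in P/F units.

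**Conclusion.** The point holds in a limited form. Following the plan as written, an investigator who knows the arm can take a patient out of the study for a reason that may be related to outcome, with no commitment to later endpoint data and with omission under 7.4.

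The 9% share follows from the planned group size and applies in full if 7.4 omits the patient. The 2.5% to 10.6% loss of precision also assumes equal SDs and one exit in total up to two in each arm. The precision loss is modest; the more important issue is that the exits may not be random. How many there would be, and what bias would result, cannot be determined from the documents. For a pilot with no power claim, this is a cheap improvement.

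**What to change.** Change the three sections together. Amending 7.4 alone would not secure the data, and amending 6.5 alone would not ensure that they are analysed.

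- **6.5:** State that an adverse event, malfunction or clinically necessary deviation leads by default to stopping the device or procedure, not to study exit. In both arms, continue P/F to 72 hours, and ventilation status, vital status and adverse events by chart review to Day 30. Take viral-load samples where consent stands and sampling is clinically acceptable. All of this applies unless consent or authorization is withdrawn.
- **6.5.1:** At the final contact, ask withdrawing participants for permission for chart review of P/F and ventilation as well as survival.
- **7.4:** State that patients who stop the device, or whom the investigator discontinues, are analysed in their randomized arm with all available data.

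The decision to stop warming stays with the clinicians. The cost is a few sentences, a little more chart abstraction, and the slight dilution worked out above: at most 9% of the mean effect for each retained patient in whom warming has no effect.
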